#### **B. Hypotheses / Research Question(s)**

Version Number: 5

Protocol Number: Pro2018001008

PI Name: [name]

Protocol Title: TENS after Cesarean Delivery

3

RESERVED FOR IRB STAMP

DO NOT MODIFY THIS SPACE

IRB ID: Pro2018001008

IRB Form Version 01/2018 Approval Date: 7/19/2022

Expiration Date: 7/18/2023

We hypothesize that patients that receive TENS therapy will report lower pain scores and request less opioid medication than the control group. We anticipate improved control in particular in the group of women with a history of opioid use.

Additionally, we believe that the TENS therapy will show benefits in other postpartum outcomes including time to bowel movement, level of sedation, and time to out of bed.

Overall, we anticipate that this pilot study will support the application of TENS therapy in postpartum pain management.

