### **1.3 Research Design and Methods**

**OVERVIEW.** This study is a pilot randomized interventional trial. Two categories of participants will be randomly assigned to an invention or control group, using a random number generator: normal cesarean without associated comorbidity, or cesarean in women with a history of opioid addiction, as defined by use of opioid replacement medications of either methadone or Subutex during pregnancy. The control group will receive usual care which is

Version Number: 5

Protocol Number: Pro2018001008

PI Name: [name]

Protocol Title: TENS after Cesarean Delivery

4

RESERVED FOR IRB STAMP

DO NOT MODIFY THIS SPACE

IRB ID: Pro2018001008

[figure not shown]
IRB Form Version: 01/2018 Approval Date: 7/19/2022

Expiration Date: 7/18/2023

standard post-operative pain management with opioids and NSAIDS. The intervention group will receive usual care plus TENS therapy beginning 8 hours after C-section and continuing to discharge. Both groups will receive medications for pain as requested or ordered by the doctor.

**RESEARCH PROCEDURES.** Patients will be identified for participation in several locations. Prenatal patients at the Rutgers Medical Group Obstetrics and Gynecology or Maternal Fetal Medicine practices, or the High Risk Obstetric Perinatal Clinic will be approached for study inclusion. Physicians that have a direct treatment relationship with the patient will inform the patient about the study and invite them to enroll. Consent for participation will be reviewed with the principal investigator and signed prior to delivery hospitalization. Randomization will follow consent, and patients randomized to intervention will have teaching performed about how to use the device at the time of consent.

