### **1.5 Sample Size Justification**

This is a pilot feasibility study to evaluate effectiveness and acceptability in our patient population of TENS use throughout delivery hospitalization. We aim to have 20 participants total: 5 in control and 5 in intervention without history of opioid addiction, and 5 in control and 5 in intervention with history of opioid addiction/misuse. This sample size is comparable to other shorter term pilot studies. This pilot study will serve as the basis for larger trials in the future, with larger sample size powered to demonstrate reduction in pain scores. We anticipate recruitment for this trial will take approximately 6-9 months.

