#### **4.3 Subject Randomization**

A random number generator will be used for randomization, with even groups randomized to no intervention, and odd groups to intervention.

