TENS and Opioid Use After Cesarean Delivery

NCT03843788

Document Type: Statistical Analysis Plan

Document Date: 7/11/2024

Statistical Analysis Plan

All outcomes will be presented using descriptive statistics; normally distributed data by the mean and standard deviation (SD) and skewed distributions by the median and interquartile range (IQR).

Primary Outcome

The primary analysis will compare intervention groups (TENS vs usual care) on mean change in pain score as measured by Visual Analog Scale (VAS) over the course of the inpatient hospital stay. Measured primary outcomes were pain ratings, number and type of pain medications used, and patient satisfaction with pain control. Fixed effects repeated measures analysis of variance was used to evaluate the differences in pain scores between groups and Mann-Whitney tests were used to examine differences in medication intake. Additionally, repeated measures correlation (RMCORR) between TENS and usual care arms with an exploratory analysis of pain behavior in individuals with SUD compared to no SUD will be performed.

Secondary outcomes

Secondary outcomes will include pain surveys at 6 weeks postoperatively, time to first bowel movement, level of sedation, and time to out-of-bed (OOB).

Missing data

Mixed-effects procedure was utilized to avoid loss of data from missing values at different time points.

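### The SAP's additional repeated measures correlation between arms names no within-woman variables and has no within-woman pairs as worded, and its SUD comparison does not address the expected larger TENS benefit with opioid history

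*SAP*

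**What the plan says.** The SAP's Primary Outcome paragraph gives the main analysis of pain as follows: "Fixed effects repeated measures analysis of variance was used to evaluate the differences in pain scores between groups". Medication intake is compared by Mann-Whitney tests. An additional analysis follows, "repeated measures correlation (RMCORR) between TENS and usual care arms", joined in the same sentence to an "exploratory analysis of pain behavior in individuals with SUD compared to no SUD will be performed". The SAP names no two variables for the correlation. It names no model for the SUD comparison and does not define SUD.

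On design, Protocol section 1.3 says "Two categories of participants will be randomly assigned to an invention or control group". The two categories are cesarean without comorbidity, and cesarean in women on methadone or Subutex during pregnancy. Section 4.3 allocates by random number, with "even groups randomized to no intervention, and odd groups to intervention". Section 1.5 sets the cells: "5 in control and 5 in intervention without history of opioid addiction", and "5 in control and 5 in intervention with history of opioid addiction/misuse".

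On the hypothesis, Protocol section 1.1.B says: "We anticipate improved control in particular in the group of women with a history of opioid use".

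**The concern.** There are two linked problems.

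- **The correlation.** RMCORR estimates the common within-person association between two measurements taken repeatedly on the same person. The SAP puts the two arms where the two measurements should be. A coefficient produced under that description would sit beside the primary result and could be read as evidence on the treatment, which it cannot be.
- **The opioid-history question.** The protocol expects TENS to help more in women with opioid history. That is a statement about a difference in treatment effect between categories. The SAP plans a comparison of women with and without SUD, which is a different quantity. The contrast that matches the expectation appears in neither document.

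**Working it through.** The documents give no correlation, alpha, effect size or power figure to reproduce. The only related number is the sample size: 2 arms × 2 categories × 5 = 20, which agrees with Protocol section 1.5.

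**1. Are there pairs to correlate?** Each woman is in one arm, so 0 of 20 have both a TENS and a usual-care score. RMCORR is r = Σxy / √(Σx² Σy²), where x and y are deviations from each woman's own mean. If x is the arm indicator, it is constant within each woman, so Σx² = 0 and r = 0/0.

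**2. What would forced pairing give?** Suppose each of 10 TENS women were paired with one of 10 usual-care women.

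- *A constant benefit is invisible.* Subtracting the same amount from every TENS score leaves each woman's deviations unchanged, so r does not move. In one simulated data set with 3 time points, r = 0.3255 with shifts of 0, 2 and 5 points alike.
- *The answer depends on the pairing.* Over 5,000 random re-pairings of that data set, r ran from −0.05 to 0.81.
- *A shared time trend creates correlation.* The inputs are the means and SDs in Table 1 of Protocol section 1.4:

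| | Intervention | Control |
|---|---|---|
| POD-0 | 0.612 (0.268) | 0.668 (0.315) |
| POD-1 | 0.362 (0.173) | 0.532 (0.280) |
| POD-2 | 0.352 (0.194) | 0.514 (0.280) |

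The women were simulated as unrelated, in 10 arbitrary pairs over 3 days. The within-woman correlation is assumed, because the documents give none. The test is t = r√(df/(1 − r²)) with df = 10 × (3 − 1) − 1 = 19.

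| Within-woman correlation | Mean r | p<0.05 |
|---|---|---|
| 0.3 | 0.20 | about 14% |
| 0.5 | 0.26 | about 21–22% |
| 0.7 | 0.35 | about 36–37% |

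With the time trend removed, mean r is about 0 and the rate is about 5%. The excess comes from pain falling after surgery in both arms.

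**3. Does SUD versus no SUD address the hypothesis?** Take illustrative mean pain scores as (usual care, TENS).

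- No history (5, 5) and history (6, 4): the SUD difference is (6 + 4)/2 − (5 + 5)/2 = 0. The difference in TENS effect is (4 − 6) − (5 − 5) = −2.
- No history (5, 4) and history (8, 7): the SUD difference is 7.5 − 4.5 = 3. The difference in TENS effect is (7 − 8) − (4 − 5) = 0.

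Either quantity can be zero while the other is not.

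**4. How precise would the right contrast be?** Assume two-sided alpha 0.05 and one summary score per woman, with effects in SD units. A difference of differences over four cells of 5 has SE = √(4/5) = 0.894 SD on 20 − 4 = 16 df. By the noncentral t:

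| Interaction (SD) | 0.5 | 0.8 | 1.0 | 1.5 | 2.0 |
|---|---|---|---|---|---|
| Power | 8% | 13% | 18% | 35% | 56% |

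About 2.67 SD is needed for 80% power. The overall 10 versus 10 comparison has SE = √(2/10) = 0.447 SD and needs about 1.33 SD. The 95% CI half-width for the interaction is about 2.12 × 0.894 = 1.90 SD.

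**The case against.** The best defence is that the phrase is shorthand: RMCORR of two within-woman variables, such as pain and time or pain and medication, estimated in each arm and then compared. That can be computed, and the SAP may have meant it. This stands as a possible intention. But the SAP does not name the variables, so an analyst cannot carry it out from the text, and the sentence needs rewriting on either reading.

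Two stronger readings are tempting, and the documents do not support them.

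- A reader might infer that the analyst is bound to pair unrelated women and would often obtain a significant result. The documents propose no such pairing. The intervention/control pairs in Protocol section 6.3 serve safety monitoring and come with no matching rule. Even under forced pairing, most simulated trials were not significant. The simulation also borrows its means and SDs from a cited trial of 30-minute TENS with physiotherapy, not continuous TENS. It illustrates the mechanism and does not predict this trial's result.
- A reader might infer that opioid history is ignored, or that RMCORR was meant to test that hypothesis. The SAP says neither. It plans a separate exploratory comparison by SUD; what is missing is the contrast of TENS effects between categories.

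It is also fair to say that this is an additional analysis in a pilot with no power calculation, and that an interaction with 5 per cell is weak. Both points stand. They limit the severity and mean that the contrast should be estimated, not tested for confirmation.

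**Conclusion.** The point holds in a limited form. As worded, the correlation has no within-woman pairs and cannot estimate a treatment difference. That follows from the parallel design and needs no numerical assumption. The planned SUD comparison does not measure whether TENS helps more in women with opioid history. The repeated measures ANOVA of pain and the Mann-Whitney comparisons of medication do not depend on either analysis.

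The forced-pairing figures (mean r 0.20 to 0.35; p<0.05 in about 14 to 37% of trials, against about 5% without a trend) rest on Table 1 and an assumed within-woman correlation of 0.3 to 0.7. They apply only if someone pairs the women arbitrarily. The power figures rest on the assumed alpha and a single score per woman. This should be corrected, but it does not threaten the main comparison.

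**What to change.** 1. Delete the correlation between arms. Alternatively, restate it as RMCORR of two named within-woman variables, for example pain score and opioid amount, estimated separately in each arm.
2. Add an arm-by-opioid-history term to the repeated-measures mixed model for pain. Define history by the protocol's baseline category (methadone or Subutex; sections 1.3 and 4.2.D) in place of the undefined SUD. This is a baseline category within which arm is assigned; it is not itself randomised.
3. Report the arm effect in each category, and the difference between the two effects, with 95% CIs. Label them exploratory and present them as estimates, not as a confirmatory test.

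The cost is a rewrite of one SAP sentence. Pain scores, medication amounts and opioid history are already recorded, so no new data are needed. The downside is wide intervals: about ±1.90 SD for the difference in effects under the assumptions above. The SAP should say so in advance.
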